4.4. Exploratory analysis

- **Describe the frequency, etiology and antibiotic resistance patterns of community-acquired bacteremia detected in patients with febrile illnesses.**
 - *Standard descriptive statistics will be used to describe the frequency, etiology and antibiotic resistance profiles of febrile patients, as determined by bacteremia.*
- **Assessing the performance and potential contribution of a rapid immunochromatographic test targeting dengue under field conditions in the DRC.**

- *Determination of diagnostic performance with standard diagnostic measures, such as sensitivity, specificity, PPV, NPV, positive likelihood ratio and negative likelihood ratio of the dengue immunochromatographic rapid test. PCR results from metagenomic analyses and secondary research (such as the HAT-ARBO study) will be used as the gold standard.*
- **Evaluate metagenomic sequencing for the detection of pathogens causing febrile illness (with primary focus on RNA viruses).**
- *This objective is not included in the statistical analysis, but will be the subject of a specific analysis at a later date.*

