1. Analysis of inflammatory biomarkers: C-reactive protein (CRP), white blood cells and their differentiation by different types of point-of-care (POC) equipment: analyzers and RDTs. An evaluation of the performance of a few TDRs for CRP will be carried out. as an additional comparative analysis. The objectives and methodology of this laboratory-only analysis is not described in a specific sub-protocol (Appendix 1). This new component will enable the future evaluation of strategies Diagnostics based on the use of RDTs for these inflammatory biomarkers, integrated into clinical routine.
2. Etiological research into febrile illnesses
  - a. Blood culture monitoring. Although pilot projects exist on both sites already, as part of a project to improve monitoring of resistance to antibiotics and clinical management (protocol approved in the DRC and the Belgium; IRB IMT 613/08, UZA CE 8/20/96), the systematic application on FIKI study populations will make it possible to evaluate bacteremia as an etiology of febrile illnesses, and to evaluate the biomarkers analyzed as factors of prediction of blood culture positivity.
  - b. Systematization of febrile illnesses using RDTs targeting specific specific pathogens: malaria and dengue fever. Unlike malaria, RDTs for dengue are poorly validated under field conditions in sub-Saharan Africa. A systematic use of dengue RDTs, and reference diagnoses (in metagenomic analyses, or other secondary research) will enable us to assess their respective roles in the diagnostic approach to diseases feverish in this context.

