## 2.3 Exploratory judgment criteria

- Frequency of bacteremia, with etiological distribution and drug resistance profiles antibiotics for identified germs
- Detection of dengue by rapid test (NS1 antigen, IgM)
- Detection and profiling of pathogens causing febrile illnesses by sequencing metagenomics

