## **9.6 Incidental discoveries**

All results of immediate laboratory analyses in the FIKI study (with the exception of TDR for dengue fever, currently being evaluated in the African context) will be communicated to the team, the patient. In general, these are analyses that should already be part of the routine management of febrile illnesses.

As explained above, however, participation in the study can lead to chance discoveries. pathogens that can give rise to chronic infections (asymptomatic for long periods),

requiring further action at the level of the individual patient. These discoveries can occur in metagenomic sequencing and secondary research.

If an endemic infection with immediate importance for management such as trypanosomiasis is detected during secondary research, the patient and medical team will be informed, and the patient will be offered a free diagnostic evaluation (and possible treatment) at a nearby referral center.

If a chronic infection (HIV, HBV, HCV, etc.) is discovered incidentally during the analyses metagenomics or subsequent secondary research), only the results considered to be will be communicated. The results of this technique are not considered conclusive for the time being (the metagenomic analysis currently being development is not yet a validated clinical laboratory test) and would require a additional confirmation through a standard clinical workup. The study teams will then be responsible for informing the participant in question and directing him or her to the care structure appropriate for the health problem detected.

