3.4. Exploratory variables

- Number of patients from whom blood cultures were taken, proportion of positive blood cultures, identification of germs from positive blood cultures and resistance

profile

- Antibiotic resistance of identified germs (per bacteremia)
- NS1 and IgM antigen results for the detection of dengue by rapid test
- Pathogens causing febrile illness by metagenomic sequencing

4. Statistical analysis

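### Minor, exploratory objective 2 only: SAP 4.4 scores the dengue rapid test (NS1 and IgM) against an RNA-based gold standard without defining a positive test or separating the two markers

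*SAP*

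**What the plan says.** The dengue item in SAP 4.4 lists sensitivity, specificity, PPV, NPV and both likelihood ratios for the rapid test and ends: "PCR results from metagenomic analyses and secondary research (such as the HAT-ARBO study) will be used as the gold standard". The next item, on evaluating metagenomic sequencing, reads: "This objective is not included in the statistical analysis, but will be the subject of a specific analysis at a later date".

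The results that make up the test are given in SAP 3.4 as "NS1 and IgM antigen results for the detection of dengue by rapid test" and in Protocol 2.3 as "Detection of dengue by rapid test (NS1 antigen, IgM". The protocol synopsis also lists IgG and describes IgG and IgM as antibodies. Protocol 5.3 names one device for all of these. Neither document states which line or lines make the test positive.

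Protocol 1.2 gives the purpose. It says that "RDTs for dengue are poorly validated under field conditions in sub-Saharan Africa" and that systematic testing, set against "reference diagnoses (in metagenomic analyses, or other secondary research", will show the role of these tests. On metagenomics, Protocol 9.6 says "The results of this technique are not considered conclusive for the time being" and that the method "is not yet a validated clinical laboratory test". The note in Protocol 5.2 describes the method as sequencing the RNA in the sample.

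Entry requires fever at presentation or documented within the preceding 24 hours, with no upper limit on how long it has lasted (synopsis and Protocol 4.3). Study blood is taken at inclusion, and Protocol 5.1 has no laboratory procedures at follow-up.

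**The concern.** A test that reads an antigen and an antibody is to be judged against detection of RNA. For NS1 the comparison is natural. For IgM it is not: the reference and the IgM line measure different things, and since fever of any duration is accepted, patients late in an illness can enrol. An IgM-positive, RNA-negative result may be a test error or may not. The inclusion sample cannot tell these apart, and there is no later study sample that could.

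A reference called a gold standard settles the matter by definition. If the IgM line counts, such a patient goes into the false-positive cell. The study is meant to inform whether dengue rapid tests are useful in this setting, so a low PPV produced by the choice of reference could count against the test without evidence that it failed.

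The second strand is the reference itself. Where it consists of sequencing, the SAP gives the top evidential rank to a technique that the protocol describes as not yet validated and whose own evaluation the SAP postpones.

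**Working it through.** The documents give no figure for this objective: no dengue prevalence, expected accuracy, IgM frequency or reference accuracy. There is nothing to reproduce. The check is therefore the 2x2 algebra, with assumed inputs that show direction only.

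**What follows without assumptions.** Three rules for a positive test fit the text.
- NS1 only: an IgM-positive, NS1-negative, RNA-negative patient is a true negative, so there is no IgM effect.
- IgM only: every IgM-positive, RNA-negative patient is a false positive.
- NS1 or IgM: the same, for those not already NS1-positive.

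The SAP does not choose among them, so the planned table cannot be built from it as written.

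**Illustration A: a test with no errors.** From the SAP: N = 1,500, taking everyone to have both results, which the documents do not promise. Assumed: 5% true dengue (75 cases), the combined test always right, and a share m of cases IgM-positive but RNA-negative.
- Scored false positives = 75m.
- Apparent specificity = 1,425/(1,425 + 75m).
- Apparent PPV = (75 − 75m)/75 = 1 − m.

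| m | scored false positives | apparent specificity | apparent PPV |
|---|---|---|---|
| 10% | 7.5 | 99.5% | 90% |
| 30% | 22.5 | 98.4% | 70% |
| 50% | 37.5 | 97.4% | 50% |

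The true values are 100% throughout. The loss is small in specificity and large in PPV.

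**Illustration B: adding IgM to an imperfect NS1.** Assumed: 75 RNA-positive and 1,425 RNA-negative, NS1 sensitivity 80% (60 true positives), IgM adding no RNA-positive patient, and IgM positive in a fraction f of RNA-negatives independently of NS1. With NS1 specificity Sp, the apparent false-positive fraction is r = 1 − Sp(1 − f). PPV = 60/(60 + 1,425r) and LR+ = 0.80/r.

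| NS1 Sp | f | r | apparent specificity | PPV | LR+ |
|---|---|---|---|---|---|
| 99% | NS1 alone | 0.0100 | 99.0% | 81% | 80 |
| 99% | 1% | 0.0199 | 98.0% | 68% | 40 |
| 99% | 3% | 0.0397 | 96.0% | 51% | 20 |
| 99% | 5% | 0.0595 | 94.05% | 41% | 13 |
| 97% | NS1 alone | 0.0300 | 97.0% | 58% | 27 |
| 97% | 1% | 0.0397 | 96.0% | 51% | 20 |

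At f = 1%, LR+ halves when NS1 specificity is set at 99% but falls only from 27 to 20 at 97%. The direction is the same in every row; the size depends on inputs that nobody has stated.

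**The case against.** **No positivity rule means no demonstrated bias.** A reader might infer that IgM-positive, RNA-negative patients will be counted as false positives. The SAP does not say that. An NS1-only rule would remove the effect, so the consequence is conditional. What stands is that two of the three possible rules produce it and nothing in the SAP excludes them.

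**The reference may be better than it sounds.** A reader might infer that the dengue test is to be judged by unvalidated sequencing. The SAP is an unofficial translation and speaks of PCR, which may mean targeted PCR, sequencing or both. The assays of the secondary study are not described, and Protocol 1.2 does not confine secondary research to RNA methods. The Protocol 9.6 statements occur in a paragraph on telling individuals about incidental chronic infections, although they are worded about the technique. This part therefore holds only so far as sequencing serves as the reference. If serology were included, the IgM problem would shrink, but the SAP sentence specifies PCR results.

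**The SAP says that it describes methods for the primary and secondary objectives.** Brief text on an exploratory aim fits that remit. This limits the weight of the point. It does not remove it, because SAP 4.4 does fix a reference and a list of measures.

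**Separate reporting leaves IgM without a headline specificity.** True. The documents contain no reference that could support one, and leaving out the discordant group would give 100% specificity by construction.

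One more inference should be avoided: that secondary research can use only plasma left over from metagenomics, so that the sources must cover different patients. Protocol 5.3 also collects dried blood spots, an additional EDTA tube and a PAXgene tube for secondary research.

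**Conclusion.** The point holds as a minor one, confined to exploratory objective 2. SAP 4.4 sets an RNA-based reference for a test that includes an antibody line, calls it a gold standard, and defines neither positivity nor analysis by marker. If IgM counts toward a positive result, apparent specificity is lowered, and PPV and LR+ more so, by patients in whom no test error has been shown. If only NS1 counts, this does not arise.

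The size is unknown. The tables above rest on assumed prevalence, accuracy and IgM frequency and do not bound the effect. That some IgM-positive, RNA-negative patients have recent dengue is general diagnostic reasoning, not a statement in the documents; the argument needs only that RNA alone cannot show them to be test errors.

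The primary objectives are unaffected. It would go too far to say the same of every secondary objective: objective 7 compares CRP and white cell values by etiology, including dengue or arbovirosis, and the SAP does not say how that class is assigned. If it used the same classification, it could be touched.

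**What to change.** In the dengue item of SAP 4.4, before database lock:

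- Replace gold standard with reference standard, and name the method: targeted PCR, sequencing or both.
- Define a positive result for each marker, and reconcile the synopsis, which lists IgG, with Protocol 2.3 and SAP 3.4, which do not.
- Report NS1 and IgM separately. Make NS1 against RNA detection the main comparison and keep all the planned measures for it.
- Cross-tabulate IgM against RNA. Show IgM-positive, RNA-negative participants as their own category, neither dropped nor counted as false positives on RNA alone.
- Show results for all participants with a reference result and also by reference source.

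A sensitivity analysis for imperfect reference accuracy would be a reasonable addition but is optional.

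The cost is wording and a few more tables; no new samples are needed. Numbers per source will be smaller: assuming 75 cases and an observed sensitivity of 80%, the Wilson 95% interval is 70-88% overall (60/75) against 61-91% for a source with 25 cases (20/25). There would be no single headline specificity or PPV for IgM.

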4.5. Subgroup analysis

On the basis of retained diagnostic hypotheses and laboratory results, a subgroup analysis will be performed to assess symptom resolution according to clinical presentation, diagnostic hypotheses and demographic variables, such as age, site, severity, diagnosis and others. As this is a stratified study, all analyses will be presented by stratum (combination of site and age group).

4.6. Multiplicity and missing data

An analysis of all available cases will be the primary analysis for all objectives. Missing data in all data points, except clinical status, will be flagged and, in cases of limited missing data, multiple imputation will be used to recover the data. A subsequent analysis with the full set of imputed data will be performed and compared to the primary analysis. Results will be adjusted for multiplicity using the Holm-Bonferroni method.
